6.2 Preparation/Handling/Storage/Accountability

6.2.1 Dose Preparation

MK-8189

There are no specific calculations or evaluations required to be performed to administer the proper dose to each participant.

MK-5720

Specific calculations or evaluations required to be performed to administer the proper dose to each participant are outlined in a separate document provided by the Sponsor. The rationale for selection of doses to be used in this study is in Section 4.3.

MK-5720 and placebo dosage form will be prepared and dosed per the instructions outlined in the Method of Preparation Document and Study Operations Manual.

6.2.2 Handling, Storage, and Accountability

The investigator or designee must confirm appropriate temperature conditions have been maintained during transit for all study intervention received, and any discrepancies are reported and resolved before use of the study intervention.

Only participants enrolled in the study may receive study intervention, and only authorized site staff may supply or administer study intervention. All study interventions must be stored in a secure, environmentally controlled, and monitored (manual or automated) area in accordance with the labeled storage conditions with access limited to the investigator and authorized site staff.

The investigator, institution, or the head of the medical institution (where applicable) is responsible for study intervention accountability, reconciliation, and record maintenance (ie, receipt, reconciliation, and final disposition records).

For all study sites, the local country Sponsor personnel or designee will provide appropriate documentation that must be completed for drug accountability and return, or local discard and destruction if appropriate. Where local discard and destruction is appropriate, the investigator is responsible for ensuring that a local discard/destruction procedure is documented.

The study site is responsible for recording the lot number, manufacturer, and expiry date for any locally purchased product (if applicable) as per local guidelines unless otherwise instructed by the Sponsor.

The investigator shall take responsibility for and shall take all steps to maintain appropriate records and ensure appropriate supply, storage, handling, distribution, and usage of study interventions in accordance with the protocol and any applicable laws and regulations.

6.3 Measures to Minimize Bias: Randomization and Blinding

6.3.1 Intervention Assignment

Participants will be assigned randomly according to a computer-generated allocation schedule.

A sample allocation table is provided below in [Table 7].

Table 7 Allocation of Participants to Treatment

Panel	N	MK-8189 Treatment Period 1	MK-5720 Treatment Period 2
Panel A	6	4 mg	35 mg
	2	Placebo	Placebo
Panel B	6	8 mg	70 mg
	2	Placebo	Placebo
Panel C	9	Less than or equal to 16 mg	Less than or equal to 140 mg
	3	Placebo	Placebo
Panel D	9	Less than or equal to 24 mg	Less than or equal to 280 mg
	3	Placebo	Placebo
Panel E	9	Less than or equal to 48 mg	Less than or equal to 560 mg
	3	Placebo	Placebo
Panel F	9	Less than or equal to 48 mg	Less than or equal to 560 mg
	3	Placebo	Placebo

The suggested doses may be adjusted downward based on evaluation of safety, tolerability and/or pharmacokinetic data observed in previous treatment periods/panels.

6.3.2 Stratification

No stratification based on age, sex, or other characteristics will be used in this study.

6.3.3 Blinding

A double-blinding technique will be used. MK-8189, MK-5720 and placebo will be prepared and/or dispensed in a blinded fashion by an unblinded pharmacist or qualified study-site personnel. The participant, the investigator, and Sponsor personnel or delegate(s) who are involved in the study intervention administration or clinical evaluation of the participants are unaware of the intervention assignments.

6.4 Study Intervention Compliance

Interruptions from the protocol-specified treatment plan require consultation between the investigator and the Sponsor and written documentation of the collaborative decision on participant management.

When participants are dosed at the site, they will receive study intervention directly from the investigator or designee, under medical supervision. The date and time of each dose administered in the clinic will be recorded in the source documents and recorded in the CRF. The dose of study intervention and study participant ID will be confirmed at the time of dosing by a member of the study-site staff other than the person administering the study intervention.

6.5 Concomitant Therapy

If there is a clinical indication for any medications or vaccinations prohibited, the investigator must discuss any questions regarding this with the Sponsor's Clinical Director. The final decision on any supportive therapy or vaccination rests with the investigator and/or the participant's primary physician. However, the decision to continue the participant on study intervention requires the mutual agreement of the investigator and the Sponsor.

Live vaccines must not be administered within 30 days prior to the first dose of study intervention, while participating in the study, and for 60 days after the last dose of study intervention.

Note: Any licensed COVID-19 vaccine (including for Emergency Use) in a particular country is allowed in the study as long as they are mRNA vaccines, replication-incompetent adenoviral vaccines, or inactivated vaccines. These vaccines will be treated just as any other concomitant therapy.

Investigational vaccines (ie, those not licensed or approved for Emergency Use) are not allowed.

Nonlive vaccines may only be administered in consultation with the Sponsor prior to or following the receipt of study intervention according to the time frames specified in Exclusion Criteria (Section 5.2).

Any medication or vaccine (including over-the-counter or prescription medicines, vitamins, and/or herbal supplements or other specific categories of interest) that the participant is receiving at the time of enrollment or receives during the study must be recorded along with:

Reason for use

- Dates of administration including start and end dates
- Dosage information including dose and frequency

Paracetamol/acetaminophen (up to 4 g per day), ibuprofen (up to 1.2 g per day) and antacids (eg, magnesium hydroxide) may be used for minor ailments without prior consultation with the Sponsor.

Medications to treat mild chronic conditions such as hypothyroidism, diabetes, high blood pressure, chronic respiratory conditions or other mild medical conditions are allowed during the study if the prescribed dose and regimen of medication are stable for at least 3 months prior to screening and there are no expected changes in co-medication during the study. Inclusion of participants being administered concomitant medications that have not been stable for 3 months must be discussed with the Sponsor. Moderate to strong inhibitors or inducers of CYP3A are not allowed as MK-8189 is being metabolized by these CYP enzymes and co-administration of inhibitors or inducers may potentially alter the metabolism and PK of MK-8189. The Sponsor Clinical Director should be contacted if there are any questions regarding concomitant or prior therapy.

6.5.1 Rescue Medications and Supportive Care

For the treatment of EPS, such as acute dystonia, all participants may be treated with an anticholinergic. If the symptoms are unresponsive to anticholinergic treatment, a benzodiazepine can be used. CRUs will be staffed with medically trained personnel with appropriate access to full service acute-care hospitals to facilitate rapid institution of medical intervention.

In case the participant presents with signs of akathisia without signs of dystonia, the participant can be treated with a β -adrenergic blocker. If symptoms do not resolve with the β -adrenergic blocker, treatment with an anticholinergic may be used. An anticholinergic may be used as first-line treatment in the case that a β -adrenergic blocker is not a preferred treatment based on a participant's medical history and/or concomitant medication.

Anticholinergics benzodiazepines and β -adrenergic blockers are often used in the treatment of EPS and are considered standard practice. Oral anticholinergic treatment is also used as concomitant medication to prevent EPS symptom with antipsychotic medication.

Participants will be washed off from their antipsychotic treatment (Section 8.1.5.1). The duration of washout period should be at least 5 days or cover at least 3 half-lives of the drug (whichever is longer) prior to Day -1 assessments in Period 1. During the washout and treatment period, a benzodiazepine and zolpidem may be used to treat withdrawal symptoms. The drugs indicated above should not be inhibitors or inducers of CYP3A and CYP2C9 (see Section 6.5 for further details), thus no effect on the PK of MK-8189 would be expected during coadministration.

In the event that the patient must be discontinued due to worsening of psychosis while on MK-5720, standard of care practice should be initiated, utilizing the lowest dose of an oral antipsychotic required to control symptoms during washout of MK-5720. Approved oral antipsychotic medications for this study are outlined in [Table 8] based on prior clinical experience with addition of oral MK-8189 to the antipsychotic medications at the dose range mentioned below and that were generally well tolerated in 2 clinical studies conducted with

oral MK-8189 (P003 and P007). The medications listed below or use of any other standard of care oral antipsychotic medications may be used following prior consultation of the PI with the Sponsor.

Table 8 Approved Oral Antipsychotic Medications

Medication Name	Total Daily Dose Range Coadministered with MK-8189	Target Daily Dose Range for Schizophrenia in Adults
Quetiapine	50 to 600 mg	50 to 750 mg ^a
Aripiprazole	7.5 to 30 mg	10 to 15 mg ^b
Risperidone	0.5 to 8 mg	2 to 8 mg ^c
Olanzapine	10 to 40 mg	5 to 20 mg ^d
Ziprasidone	60 to 80 mg	40 to 200 mg ^e
Lurasidone	60 to 80 mg	40 to 160 mg ^f

^a [U.S. Prescribing Information 2020]
^b [U.S. Prescribing Information 2017]
^c [U.S. Prescribing Information 1993]
^d [U.S. Prescribing Information 2011]
^e [U.S. Prescribing Information 2010]
^f [U.S. Prescribing Information 2013]

For patients who may experience anxiety during an MRI scan and require prophylaxis, the investigator may use a short to intermediate duration benzodiazepine, such as lorazepam, if deemed necessary and after prior consultation with the Sponsor.

6.6 Dose Modification (Escalation)

All dose-escalation decisions will be made jointly by the investigator and the Sponsor. Members of the Sponsor safety review team will include: the trial clinical director, trial clinical scientist, senior level clinical director and trial biostatistician. Additional Sponsor attendees may include a clinical research associate and a pharmacologist. The Sponsor safety review team will obtain input from the investigator regarding his/her evaluation of safety and tolerability from the previous dosing period and his/her recommendation to dose escalate in the next panel.

Each dose-escalation decision will occur after at least 8 (Panels A and B) and 12 (Panels C through F) evaluable participants have completed the previous dose level (participants will be randomized to receive MK-5720 or placebo in a 3:1 ratio, respectively).

Dose-escalation decisions will be based on blinded key safety variables, with summary statistics as needed. Safety variables will include, vital signs, 12-lead ECG, laboratory safety tests, AE, and neurological assessments from the previous dose levels up to at least 14 days postdose. PK data may be included in the dose-escalation decisions (Section 2.1 and Section 2.2).

If, as judged by the Sponsor and investigator, the safety and tolerability data do not justify dose escalation, the dose will not be increased as planned. Instead, participants may:

- receive the same dose level to further explore safety and tolerability at that level,
- receive a lower dose of the study intervention (with or without food),
- receive the same or lower dose as a divided dose, or
- dosing may be stopped.

Participant discontinuation criteria are outlined in Section 7.

6.6.1 Stopping Rules

The following stopping rules will be used during the conduct of this study.

If any of the below stopping rules are met, the study will be paused, and no further dosing will occur until the Sponsor has reviewed the totality of data available. To continue the study (on joint agreement with the Sponsor and investigator), a substantial amendment will be submitted for approval.

1. An individual participant reports an SAE considered related to the study intervention by the investigator.
2. Two (2) or more participants within a Panel (at the same dose level) report Severe Nonserious AEs considered related to the study intervention by the investigator.

If any of the above stopping rules are met, subsequent higher doses will be lowered based on joint agreement of the Sponsor and investigator in order for the study to continue.

3. Should the emerging PK (mean) data indicate that the maximum clinical exposure (C_{max} or AUC), as defined in Section 4.3 will be exceeded, subsequent higher doses will be adjusted based on joint agreement of the Sponsor and investigator.

6.7 Intervention After the End of the Study

There is no study-specified intervention after the end of the study.

6.8 Clinical Supplies Disclosure

This study is blinded but supplies are provided as open label; therefore, an unblinded pharmacist or qualified study-site personnel will be used to blind supplies. Study intervention identity (name, strength, or potency) is included in the label text; random code/disclosure envelopes or lists are not provided.

The emergency unblinding call center will use the intervention randomization schedule for the study to unblind participants and to unmask study intervention identity. The emergency unblinding call center should only be used in cases of emergency (see Section 8.1.10).

See Section 8.1.10 for a description of the method of unblinding a participant during the study, should such action be warranted.

6.9 Standard Policies

Not applicable

7 DISCONTINUATION OF STUDY INTERVENTION AND PARTICIPANT WITHDRAWAL

7.1 Discontinuation of Study Intervention

In clinical studies with a single intervention, discontinuation of study intervention can only occur before the intervention. Therefore, participants who receive a single-dose intervention cannot discontinue study intervention.

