3 HYPOTHESES, OBJECTIVES, AND ENDPOINTS

Hypotheses are aligned with objectives in the Objectives and Endpoints table.

The following objectives will be evaluated in participants with schizophrenia.

Primary Objective	Primary Endpoint
To evaluate the safety and tolerability of single-ascending doses of MK-5720 long-acting injectable administered intramuscularly in participants with schizophrenia.	Adverse Events Study discontinuation due to adverse events
To assess the plasma pharmacokinetics of MK-5720 and MK-8189 following single doses of MK-5720 long-acting injectable administered intramuscularly in participants with schizophrenia. <small>CCI</small>	Plasma MK-5720 AUC0-last, AUC0-inf, Cmax, Tmax, CL/F, Vz/F and apparent terminal t1/2 Plasma MK-8189 AUC0-28d, AUC0-inf, Cmax, Tmax, C28d, CL/F, Vz/F and apparent terminal t1/2
To evaluate the safety and tolerability of multiple once-daily oral doses of MK-8189 in participants with schizophrenia.	Adverse Events Study discontinuation due to adverse events
Secondary Objectives	Secondary Endpoints
To assess the plasma pharmacokinetics of MK-8189 following single doses of MK-5720 long-acting injectable administered intramuscularly in participants with schizophrenia <small>CCI</small>	<small>CCI</small>

To compare the effect of the site of administration of MK-5720 long-acting injectable on plasma pharmacokinetics of MK-5720 and MK-8189 following a single dose of MK-5720 long-acting injectable administered intramuscularly in the gluteal muscle relative to its administration in the deltoid muscle.
 
Estimation: The effects of the site of administration on plasma pharmacokinetics of MK-5720 and MK-8189 following a single dose of MK-5720 long-acting injectable administered intramuscularly in the gluteal muscle will be estimated and compared to a single dose of MK-5720 long-acting injectable administered intramuscularly in the deltoid muscle.
	
Plasma MK-8189 AUC0-28d, AUC0-inf, Cmax, Tmax, C28d, CL/F, Vz/F and apparent terminal t1/2
 
Plasma MK-5720 AUC0-last, AUC0-inf, Cmax, Tmax, CL/F, Vz/F and apparent terminal t1/2

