MRI exam will be incorporated in 2 panels at or 1 dose level below the highest dose of MK-5720 LAI that are administered IM in the deltoid and gluteal muscles to visualize the injection site depot using multislice spin-echo T2-weighted and assess the location of the depot in the muscle and to quantify drug depot characteristics, including volume and surface area over time. This information will be utilized to better understand any differences in PK between patients and to build models to better predict human PK from preclinical animal models in subsequent clinical studies.

Decision to dose participants with MK-5720 in any given panel will be based on demonstrating acceptable tolerability in individual participants with oral MK-8189 from the oral tolerability run-in period and based on key safety variables including AEs, VS, 12-lead ECGs, laboratory safety tests, neurological and physical examinations, and C-SSRS. The decision for a participant to proceed to Period 2 will be a joint decision between the PI and the Sponsor. Dose escalation decisions for MK-5720 will be based on key safety variables including AEs, VS, 12-lead ECGs, laboratory safety tests, neurological and physical examinations, C-SSRS, and local and systemic reactions assessed in Period 2. The decision to proceed to the next higher dose level will be based upon acceptable safety of MK-5720 at the previous dose. When available, plasma PK data will be reviewed to aid dose escalation decisions. For dose escalation to Panel B, the decision to proceed will be based on 14 days of safety and tolerability data from Panel A. ^{CCI} [REDACTED]

[REDACTED] Plasma concentrations of MK-5720 from the preceding panels will be determined at the allocated PK breaks to ensure that the NOAEL AUC exposure limits are not exceeded at the doses in the subsequent panels. Similarly, plasma concentrations of MK-8189 from the preceding panels will also be determined at the allocated PK breaks to ensure that MK-8189 exposures do not exceed exposures observed with oral MK-8189 at doses that are generally well tolerated in participants with schizophrenia. Dose escalation decisions for Panels C through F will be informed by safety, tolerability, and PK data from all patients in the prior panel through 28 days postdose.

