8.1.9 Discontinuation and Withdrawal

The investigator or study coordinator must notify the Sponsor when a participant has been discontinued/withdrawn from the study. If a participant discontinues for any reason at any time during the course of the study, the participant may be asked to return to the clinic (or be contacted) for a poststudy visit as per the number of days described in Section 1.3 to have the applicable procedures conducted. However, the investigator may decide to perform the poststudy procedures at the time of discontinuation or as soon as possible after discontinuation. If the poststudy visit occurs prior to the safety follow-up time frame as specified in Section 8.4.1, the investigator should perform a follow-up telephone call at the end of the follow-up period (Section 8.4.1) to confirm if any AEs have occurred since the poststudy clinic visit. Any AEs that are present at the time of discontinuation/withdrawal should be followed in accordance with the safety requirements outlined in Section 8.4.

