8.4 Adverse Events, Serious Adverse Events, and Other Reportable Safety Events

The definitions of an AE or SAE, as well as the method of recording, evaluating, and assessing causality of AE and SAE and the procedures for completing and transmitting AE, SAE, and other reportable safety event reports can be found in Appendix 3.

Adverse events, SAEs, and other reportable safety events will be reported by the participant (or, when appropriate, by a caregiver, surrogate, or the participant's legally authorized representative).

The investigator and any designees are responsible for detecting, documenting, and reporting events that meet the definition of an AE or SAE as well as other reportable safety events. Investigators need to document if an SAE was associated with a medication error, misuse, or abuse.

Investigators remain responsible for following up AEs, SAEs, and other reportable safety events for outcome according to Section 8.4.3. The investigator, who is a qualified physician, will assess events that meet the definition of an AE or SAE as well as other reportable safety events with respect to seriousness, intensity/toxicity, and causality.

8.4.1 Time Period and Frequency for Collecting AE, SAE, and Other Reportable Safety Event Information

AEs, SAEs, and other reportable safety events that occur after the participant provides documented informed consent, but before intervention/randomization, must be reported by the investigator under any of the following circumstances:

- if the participant is receiving placebo run-in or other run-in treatment,
- if the event causes the participant to be excluded from the study,
- if it is the result of a protocol-specified intervention, including, but not limited to washout or discontinuation of usual therapy, diet, placebo, or a procedure.

From the time of intervention randomization through 14 days after cessation of intervention, all AEs, SAEs, and other reportable safety events must be reported by the investigator.

Additionally, any SAE brought to the attention of an investigator any time outside the period specified in the previous paragraph also must be reported immediately to the Sponsor if the event is considered related to study intervention.

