9.3 Analysis Endpoints

9.3.1 Primary Endpoints

Safety: Primary safety endpoints will include all types of adverse events and discontinuation of study intervention due to adverse event(s), in addition to laboratory safety tests, ECGs, and vital signs. Baseline is defined as measurements obtained pre-dose Day 1. These endpoints will be calculated for both periods (oral run-in doses of MK-8189 and IM single-ascending doses of MK-5720).

Pharmacokinetics: The pharmacokinetic variables of plasma MK-5720 AUC0-last, AUC0-inf, Cmax, Tmax, CL/F, Vz/F and apparent terminal t1/2 will be evaluated along with the plasma MK-8189 AUC0-28d, AUC0-inf, Cmax, Tmax, C28d, CL/F, Vz/F and apparent terminal t1/2. These PK endpoints apply to Period 2 (IM single-ascending doses of MK-5720).

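### Under 7.1, the discontinuation endpoint in 9.3.1 can only be zero after the injection, and no rule secures 55 days of follow-up for injected participants removed early

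*Combined protocol and SAP*

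**What the plan says.** **Endpoint.** Section 9.3.1 lists as primary safety endpoints "all types of adverse events and discontinuation of study intervention due to adverse event(s", together with laboratory tests, ECGs and vital signs. It adds: "These endpoints will be calculated for both periods (oral run-in doses of MK-8189 and IM single-ascending doses of MK-5720". Section 7.1 says that in a single-intervention study discontinuation is possible only before dosing, and that "participants who receive a single-dose intervention cannot discontinue study intervention". Section 3 and the synopsis word the endpoint differently: "Study discontinuation due to adverse events".

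The study has two interventions. Seven daily oral doses (Period 1) are followed by one injection (Period 2), and tolerating the first governs the second: "Decision to dose participants with MK-5720 in any given panel will be based on demonstrating acceptable tolerability in individual participants with oral MK-8189" (Section 4.1). Sections 4.2.1.2, 6.5.1 and 8.3.5.1 provide for removing participants for severe or worsening psychosis or for suicidality, and 6.5.1 refers to patients already on MK-5720.

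**Follow-up.** Sections 4.3.2 and 4.3.3 say participants will be followed for at least 55 days, about five half-lives of MK-8189 released from the depot. The operative rules are:

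- Section 8.4.1: from randomization "through 14 days after cessation of intervention, all AEs, SAEs, and other reportable safety events must be reported".
- Section 8.1.9, on discontinuation for any reason: "the participant may be asked to return to the clinic (or be contacted) for a poststudy visit". Poststudy procedures may instead be done at the time of discontinuation. If the poststudy visit precedes the end of the 8.4.1 window, a telephone call should be made when that window closes.
- Section 8.10.4: a poststudy visit about 14 days after the last study procedure (14 ± 2 days in Section 1.3.2).

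**The concern.** The two parts have a common root: discontinuation rules written for a single-intervention study are applied to an oral run-in followed by a depot that cannot be withdrawn.

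First, the statistical section names a primary safety endpoint that Section 7.1 rules out once the injection is given. A panel could have participants taken out of the study for AEs after the injection while the 9.3.1 endpoint shows none. What is reported as the primary endpoint would depend on which section the programmer followed.

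Second, Section 4.2 justifies the run-in by the inability to lower MK-8189 exposure after the injection. Participants removed early for tolerability are those for whom late AE data matter most, yet the rules that apply to them are tied to a 14-day window or to the last procedure, not to the time since injection.

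**Working it through.** **The plan's own figures**

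- Planned N (Section 1.2, Table 1; Table 7): 2 × (6 + 2) + 4 × (9 + 3) = 64, as stated. Active: 2 × 6 + 4 × 9 = 48. Placebo: 2 × 2 + 4 × 3 = 16.
- Follow-up: the last PK sample is at 1320 h, and 1320 / 24 = 55 days postdose. Dosing is on Day 1, so this is Day 56. At a half-life of about 10 days, 55 / 10 = 5.5 half-lives, in line with the stated approximation of 5.
- Completers: Day 56 + 14 = Day 70 for the poststudy visit.

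**Part A: applying 7.1 to 9.3.1**

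1. The event counted by 9.3.1 is discontinuation of study intervention because of an AE.
2. Period 2 intervention is one injection (Section 4.1).
3. Under 7.1 that event cannot occur once the injection is given.
4. The Period 2 count among injected participants is therefore fixed at 0/48 on active and 0/16 on placebo, if all 64 are injected.
5. Under Section 3 the event is leaving the study because of an AE, which Sections 4.2.1.2, 6.5.1 and 8.3.5.1 foresee. That count can exceed zero.
6. In Period 1 the 9.3.1 wording still works, because seven daily doses can be stopped. But 7.1 gives no rule for stopping them, or for withholding the injection after the run-in.

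**Part B: when follow-up ends for an injected participant removed early**

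1. Section 8.4.1 window. Cessation of intervention is not defined for a depot. If it means the injection, the window closes on Day 1 + 14 = Day 15. That is 56 − 15 = 41 days before Day 56. Section 4.3.3 says the 14-day review period allows the MK-8189 peak to be reached, so mandatory reporting could end near the peak.
2. Section 8.1.9. The return visit is optional, and the back-up call is tied to the same 8.4.1 window, so it adds nothing beyond step 1.
3. Section 8.10.4, if applied. For a last procedure on Day L the visit falls on Day L + 14, and the shortfall to Day 56 is 56 − (L + 14) = 42 − L.

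| Last procedure | 8.10.4 visit | Days short of Day 56 |
|---|---|---|
| Day 8 | Day 22 | 34 |
| Day 22 | Day 36 | 20 |
| Day 29 (28 days postdose, planned end of domiciling) | Day 43 | 13 |
| Day 36 | Day 50 | 6 |
| Day 43 | Day 57 | none |

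The ±2-day window moves each nonzero shortfall by at most 2 days either way. Nominally, only a last procedure on Day 42 or later reaches Day 56.

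4. Other provisions. Table 9 asks for all AEs through the protocol-specified follow-up period, which is not defined for someone stopped early. Section 8.4.3 requires follow-up of AEs already reported. Related SAEs that come to notice later remain reportable. None of these requires anyone to look for new nonserious AEs up to Day 56.

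**The case against.** The strongest reply on Part A is that 7.1 is template text for single-intervention studies and fits poorly here. Section 8.1.10 still speaks of discontinuing unblinded participants from study intervention without limiting that to Period 1. The list in 9.3.1 is worded as inclusive, and Section 9.2 refers back to Section 3 for objectives, so the study-level endpoint is not lost. This stands in part: it shows the mismatch is easy to repair. It does not remove it, because 9.3.1 is the text that defines what is calculated.

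A reader might infer that AE-related discontinuations after the injection would go unrecorded. The documents do not support that. Section 8.1.9 obliges the site to notify the sponsor of every discontinuation, Table 9 requires all AEs to be reported through follow-up, and Section 8.4.7 makes extrapyramidal symptoms leading to study discontinuation an event of clinical interest.

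On Part B, one might cite 8.10.3, which leaves schedule procedures to discretion, as making visits optional for all injected participants. That section covers people who discontinue treatment; on a literal reading of 7.1 it cannot apply after the injection. Those who remain in the study stay on the full schedule. The gap is confined to participants removed from the study without withdrawing consent. It is also fair that the 55 days appear in dose and design rationale, that the schedule meets them for completers, and that 8.3.5.1 requires clinical follow-up care after removal for suicidality. That care has no stated duration and is not AE data collection.

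**Conclusion.** Both parts hold, with limited consequences.

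**Part A.** Followed as written, 7.1 and 9.3.1 fix the Period 2 count at zero for injected participants, against an endpoint in Section 3 that can vary. The figures 0/48 and 0/16 assume that everyone planned is injected. A reader might infer that dose escalation is compromised. It is not: escalation under 6.6 and the stopping rules in 6.6.1 use other safety data, and the safety analysis in 9.5.1 is descriptive. The effect is on the reported primary endpoint.

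**Part B.** No rule secures 55 days for an injected participant removed early who has not withdrawn consent. AE reporting could end at about Day 15 if cessation means the injection. If 8.10.4 is applied, a last procedure on Day 29 leaves 13 days uncovered. A reader might extend this to all participants, but completers are covered to about Day 70. The documents give no discontinuation rate, so no number of affected participants is claimed.

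Section 6.6 says "Participant discontinuation criteria are outlined in Section 7", and Section 7 holds none beyond consent withdrawal. This does not mean that the trial lacks criteria, since they stand in 4.2.1.2, 6.5.1, 8.1.10 and 8.3.5.1. It is missing detail, not a further error.

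**What to change.** 1. **Section 9.3.1:** for Period 2, use study discontinuation due to AEs, as in Section 3. For Period 1, count oral dosing stopped, or the injection not given, because of an AE.
2. **Section 7.1:** limit the statement to the Period 2 injection.
3. **Section 8.4.1:** for injected participants, run the AE reporting window through the poststudy contact 14 days after Day 56 (about Day 70).
4. **Section 8.1.9:** for injected participants who leave early without withdrawing consent, require at least AE and safety contacts at Day 56 and about Day 70, by telephone if needed. Leave PK and other procedures to investigator discretion.

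The cost is wording in four sections and, as a minimum, two contacts for each affected participant, some of whom may be acutely ill. Consent withdrawal under 7.2 is unaffected.
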